In 2014, men who have sex with men (MSM) accounted for 70% of new HIV diagnoses in the United States, and MSM are the only US population in which new HIV infections are rising.¹⁰ Black and Latino men are at particularly high risk, with HIV infection rates estimated to be 6.6 and 2.9 fold higher than among White men. Disparities in HIV prevalence increased in 2008-2011, and grew fastest in the youngest age groups.¹¹ Young MSM (YMSM) accounted for nearly 20% of the estimated HIV diagnoses nationwide and over 80% of new HIV infections among youth in 2014. Furthermore, Black and Latino YMSM accounting for 55% and 33% of HIV infections among YMSM, respectively.¹⁰ Despite the promise of PrEP in preventing HIV acquisition among YMSM, PrEP uptake has been low in this vulnerable population. According to national prescription data, youth under 24 are the least likely to initiate PrEP, with only 9% of PrEP initiations in 2015 occurring in this age group.¹² In a recent national survey, only half of YMSM aged 15-24 had heard of PrEP, and 1.7% had ever used PrEP.¹³ Demonstration projects also highlight challenges with PrEP uptake and adherence. In the US Demo Project of 550 MSM, only 20% were age 25 or under, and PrEP uptake was lower among younger, non-white. and less educated persons.¹⁴ In multivariate analysis, the only independent predictors of adherence as measured by tenofovir diphosphate levels in dried blood spots were Black race (adjusted odds ratio, aOR 0.28, 95% CI 0.12-0.64) and enrollment in Miami (aOR 0.32, 95% CI 0.17-0.60).¹⁵ Self-reported adherence, pill counts, and medication possession ratios did not completely explain the disparities in TFV-DP levels. Similar findings were seen in the ATN 110 study of YMSM aged 18-22, where PrEP uptake was only 16%, and PrEP adherence was lower among Black YMSM and declined overall during follow-up, particularly with less frequent visits.¹⁶ Clearly, future PrEP studies must include sizeable numbers of African American, Latino, and young MSM, who are at high risk for HIV and may require timely adherence support, triggered by an accurate measure of adherence. Additionally, studies of on-demand (or 2-1-1) PrEP, in which 2 doses of TDF/FTC PrEP are taken in the 24 hours prior to sex, and 1 dose each taken 24 and 48 hours later, have demonstrated promise in a randomized study[refs] and

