5.3 Randomization

Participants will be randomized in a 2:1 ratio to the intervention (N=67) or control (N=33) conditions, using randomly-permuted blocks of randomly selected size 3 and 6, stratified by site (San Francisco, Atlanta). The randomization scheme will be generated and archived by the study statistician, and implemented in RedCap.

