6.2 Statistical Analysis

6.2.1 Primary Objectives

The primary objectives of the study are:

1. To assess the effect of DOT Diary on PrEP adherence as measured by TFV-DP in DBS among young MSM initiating PrEP

We will use GEE logistic models to estimate the average effect of assignment to DOT Diary on repeated TFV-DP levels ≥700 fmol/punch, which are consistent with taking 4-7 PrEP doses per week. In exploratory analyses, we will examine whether the between-group difference increases over time. We will also use analogous GEE linear models to estimate the effects of D2 on log-transformed TFV-DP levels, as well as GEE proportional odds models for an ordinal outcome defined as TFV-DP levels consistent with <2, 2-3, and 4-7 doses per week, using cut-points determined by pharmacokinetic benchmarks established through directly-observed dosing.²⁹

Minimum detectable effects (MDEs). We used data from the EPIC study to estimate the baseline level and intraclass correlation (ICC) of the repeated binary measures of DBS TFV-DP levels \geq 700 fmol/punch as 60% and 0.69 respectively, and retention of 80% of participants at 24 weeks. Under these assumptions, we will have 80% power in 2-sided tests with a type-I error rate of 5% to detect average between-group differences in adherence of 23 percentage points.

2. To evaluate the concordance of TFV-DP and FTC-TP in DBS with adherence measured by DOT Diary

Validation of DOT will focus on concordance between aDOT-based assessments of PrEP adherence by the AiCure device with four DBS measurements:

- a. We will use a pharmacokinetic (PK) model with parameters estimated in the DOT-DBS Study (NCT02022657) to calculate the expected TFV-DP levels when each DBS is obtained, based on the aDOT-based pattern of pill-taking over the previous 6 weeks. We will then estimate the correlation between these predictions and observed TFV-DP levels based on DBS, and scatterplot the two measures against each other, with a Lowess smooth. As an additional measure of concordance, we will estimate the proportion of 90% prediction intervals obtained from the PK model that include the measured DBS TFV-DP levels.

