DOT Diary Longitudinal Pilot Statistical Analysis Plan

NCT03771638

PI: [name] Date: April 5, 2019

Statistical Analysis Plan

Primary Objectives

To assess the effect of DOT Diary on PrEP adherence as measured by TFV-DP in DBS among young MSM initiating PrEP. We will use GEE logistic models to estimate the average effect of assignment to DOT Diary on repeated TFV-DP levels ≥700 fmol/punch, which are consistent with taking 4-7 PrEP doses per week. In exploratory analyses, we will examine whether the between-group difference increases over time. We will also use analogous GEE linear models to estimate the effects of D2 on log-transformed TFV-DP levels, as well as GEE proportional odds models for an ordinal outcome defined as TFV-DP levels consistent with <2, 2-3, and 4-7 doses per week, using cut-points determined by pharmacokinetic benchmarks established through directly-observed dosing.²⁸ To help with interpretation of these results, retention in the study will at each 6-week visit will be reported. Minimum detectable effects (MDEs). We used data from the EPIC study to estimate the baseline level and intraclass correlation (ICC) of the repeated binary measures of DBS TFV-DP levels ≥700 fmol/punch as 60% and 0.69 respectively, and retention of 80% of participants at 24 weeks. Under these assumptions, we will have 80% power in 2-sided tests with a type-I error rate of 5% to detect average between-group differences in adherence of 23 percentage points.

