Client Satisfaction Questionnaire (CSQ-8) adapted for use in the DOT Diary Longitudinal pilot.²⁹ Average values of our measures of acceptability and ease of use will be estimated with 95% confidence intervals. *MSEs.* The estimated sample of 54 participants providing end of study data will allow us to estimate mean SUS and CSQ-8 scores within MSEs of 0.27 standard deviations (SDs).

Secondary Objectives

To assess PrEP coverage of sexual acts (prevention-effectiveness adherence) as measured by DOT Diary. We will estimate the probability of coverage of condomless receptive sexual acts in each period, with sexual acts treated as trials, and coverage as success. Confidence intervals will be obtained using GEE binomial models, with robust standard errors will be used to account for within-subject correlation as well as over-dispersion of the binomial outcome. *MSEs.* We also used EPIC data to estimate the average number of condomless receptive sexual acts per participant as ~7. Under this assumption, we will be able to estimate coverage probabilities within MSEs of 4-10 percentage points, depending on coverage levels and the ICC of coverage across episodes.

To evaluate the daily use of the DOT and diary components of DOT Diary through 24 weeks of follow-up. We will estimate the average use of DOT and the diary, as proportions of days and weeks on study, respectively. In the primary ITT analysis, participants will be included in the denominator through 24 weeks, regardless of dropout. In a per-protocol analysis, participants will be omitted from the denominator after dropout. *MSEs.* Proportions will be estimated within MSEs of 7-12 percentage points, depending on the sample proportions.

Subgroup analyses. Four pre-specified subgroup analyses will conducted in which interaction terms will be added to the primary GEE logistic models for protective DBS levels, to assess modification of treatment effects by 1. site; 2. age (categorized as <25 and 25+); 3. race/ethnicity, categorized as African American or Latinx vs White or other; and 4. prior PrEP use. Within-subgroup effect estimates will be presented only if the corresponding omnibus test for treatment-subgroup interaction is statistically significant at P<0.15, and results will be presented as exploratory.

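### Free improvement: pre-specify site and race/ethnicity as main effects in the primary GEE model, which names no baseline covariate

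*SAP*

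**What the plan says.** The SAP (Primary Objectives) defines the primary analysis in one sentence: "We will use GEE logistic models to estimate the average effect of assignment to DOT Diary on repeated TFV-DP levels ≥700 fmol/punch". Protocol Section 6.2.1 has the same text. Neither names a baseline covariate, not even site, which is the stratification factor.

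Protocol Section 5.3 has participants "randomized in a 2:1 ratio to the intervention (N=67) or control (N=33) conditions", in permuted blocks stratified by site alone.

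Protocol Section 1.0 says that in the US PrEP demonstration project the only independent predictors of adherence, measured by TFV-DP in dried blood spots, "were Black race (adjusted odds ratio, aOR 0.28, 95% CI 0.12-0.64") and enrollment in Miami (aOR 0.32, 95% CI 0.17-0.60). It adds that a study of men aged 18-22 also found lower adherence among Black participants.

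In the SAP, race/ethnicity enters only as one of four exploratory interaction analyses: "race/ethnicity, categorized as African American or Latinx vs White or other".

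The power statement takes "DBS TFV-DP levels ≥700 fmol/punch as 60% and 0.69 respectively" as the baseline level and ICC, with 80% retention, and claims 80% power for "average between-group differences in adherence of 23 percentage points".

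**The concern.** The protocol cites evidence that a characteristic the trial already collects predicts adherence on the same analyte and matrix as the primary outcome. Neither the randomization nor the primary model uses it. Section 4.0 aims for at least 50% African American or Latino participants, so the sample should be mixed.

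With 33 controls, the racial mix of the arms will differ by chance. An unadjusted model leaves that explainable variation in the standard error. What is at stake is precision in a small trial whose results feed a larger one. There is also the risk that a visible imbalance prompts an unplanned adjustment, which would carry less weight than a planned one.

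**Working it through.** **Inputs from the documents.** Arms of 67 and 33; 60% baseline level; ICC 0.69; 3.59 samples per person (SAP concordance objective, stated for the intervention arm and applied here to both arms); two-sided 5%; aOR 0.28 (0.12-0.64).

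**Assumptions.** The Black share is not given, so 25-50% is used. The aOR is taken to carry over to this trial and this cut-point. The 60% is taken as the level for the whole control arm.

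**1. Reproduce the plan's figure.**
- Variance factor for a person's mean: (1 + 2.59 × 0.69)/3.59 = 0.776.
- Effective sizes: 33/0.776 = 42.5 and 67/0.776 = 86.3.
- A two-proportion test with pooled variance, 60% against 83%, gives power 0.800 and a minimum detectable effect of 23.0 points. The stated figure reproduces without any covariate.

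**2. Gap by race.** Let q be the Black share, and solve q·pB + (1−q)·pN = 0.60 with odds(pB)/odds(pN) = aOR. At q = 0.5 and aOR 0.28 this gives pN = 74.7% and pB = 45.3%, a gap of 29.4 points.

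**3. Variance explained and power.**
- R² = q(1−q)·gap²/(0.24 × 0.776). At q = 0.5: 0.25 × 0.294²/0.186 = 0.116.
- SE ratio = √(1−R²) = 0.940.
- New minimum detectable effect = 23.0 × 0.940 = 21.6 points.
- New power = Φ(2.80/0.940 − 1.96), about 84.6%.

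| aOR | Black share | Adherence, other / Black | R² | SE ratio | MDE (points) | Power |
|---|---|---|---|---|---|---|
| 0.28 | 25% | 67.7% / 37.0% | 9.5% | 0.951 | 21.9 | 83.8% |
| 0.28 | 33% | 70.1% / 39.6% | 11.0% | 0.943 | 21.7 | 84.4% |
| 0.28 | 50% | 74.7% / 45.3% | 11.6% | 0.940 | 21.6 | 84.6% |
| 0.64 | 25% | 62.7% / 51.8% | 1.2% | 0.994 | 22.9 | 80.5% |
| 0.64 | 50% | 65.3% / 54.7% | 1.5% | 0.992 | 22.8 | 80.6% |
| 0.12 | 25% | 72.1% / 23.7% | 23.6% | 0.874 | 20.1 | 89.3% |
| 0.12 | 50% | 83.0% / 37.0% | 28.4% | 0.846 | 19.5 | 91.2% |

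At aOR 0.28, 1/(1−R²) is 1.105 to 1.132, which is worth about 10-13 extra participants per 100.

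**4. Simulation** (logistic GEE with robust SE, 3000 trials per scenario, true difference about 23 points, without and then with a Black indicator).
- aOR 0.28: power 78.1% to 81.1% (25% Black), 76.6% to 80.6% (33%), 78.5% to 81.9% (50%). That is a gain of 3-4 points, slightly below the formula.
- aOR 0.64: 79.4% to 79.6% (25%) and 78.9% to 79.9% (50%).
- aOR 0.12: 76.3% to 83.9% (50%).
- In a separate simulation whose comparator already contained site, adding race at aOR 0.28 cut the variance by about 6-8% and raised power from 78-80% to 81-83%.

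**5. Size of chance imbalance.** The SD of the between-arm difference in Black share is √(q(1−q)(1/33 + 1/67)), or 9.2 points at 25% and 10.6 at 50%. Multiplied by the gap, that is 2.8-3.1 points in the effect estimate. The unadjusted SE with no effect is √(0.24 × 0.776 × (1/33 + 1/67)) = 9.2 points. At 25% Black, 2.83²/9.18² = 9.5%, which is the R² above. The imbalance is therefore a component of the unadjusted SE and does not come on top of it.

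**6. The SAP's pooled category.** Suppose half of a 50% pooled group is Black and Latino men do not differ from the rest. The pooled group then averages (37.0 + 67.7)/2 = 52.4%, against 67.7%, a gap of 15.3 points. R² = 0.25 × 0.153²/0.186, about 3%, and power is about 81%. With Black race coded separately, the same mix gives 9.5% and 83.8%.

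**The case against.** The strongest reply is that nothing is broken. A comparison of randomised arms without covariates is valid, and its standard error already includes chance imbalance. The stated power holds, and this is a pilot. All of that stands. Simulated type I error was 0.047-0.053 unadjusted and 0.047-0.054 adjusted at aOR 0.28 and 0.64. At 0.12 it was 0.054 and 0.061, so part of the adjusted model's advantage at that extreme comes from a test that rejects slightly too often.

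A reader might infer several stronger points that the documents do not support:
- **That the protocol calls race the strongest predictor of this very outcome.** It lists two predictors without ranking them (0.28 and 0.32, with overlapping intervals), and the background does not give the 700 fmol/punch cut-point for that analysis.
- **That imbalance biases the result, or that the trial misses its own power target.** Steps 1 and 5 show neither.
- **That race is ignored.** It is a pre-specified effect modifier, although exploratory and in a pooled category.
- **That every available baseline factor should go in.** The cited multivariable analysis found only race and Miami enrollment to be independent predictors, which gives no support for age. No prognostic evidence is cited for prior PrEP use, which may be rare because PrEP-naïve men are prioritised. In simulation (4000 runs per scenario; both factors assumed non-prognostic), a model with three-level race, age and prior PrEP use had power of 0.817-0.822, against 0.818-0.824 for site plus a Black indicator. Its null rejection was 0.055-0.061, against 0.046-0.055 unadjusted. Up to 3% of runs with a 23-point effect failed or gave extreme coefficients.

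The conditional odds ratio is also a fair worry: adding race changes what the odds ratio means. A standardised risk difference deals with that.

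**Conclusion.** This is a free improvement, not an error. The primary model leaves out a covariate that the protocol's own background shows to be prognostic, at a modest cost in precision. At aOR 0.28, power at 23 points goes from about 80% to about 83-85%. The gain is about 1 point or less at the upper confidence limit of 0.64. At the lower limit of 0.12 it is about 9-11 points by formula, and about 8 in the one scenario simulated there.

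The absence of covariates and the single stratification factor can be read directly from the documents. The size of the gain rests on an assumed Black share of 25-50%, and on an adjusted odds ratio from another cohort holding here at the 700 fmol/punch cut-point. The simulations used a binary Black indicator, with and without site. Site plus three-level race/ethnicity was not itself simulated; its extra term should change little but was not tested.

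**What to change.** Before unblinded analysis, amend the SAP's primary objective, and protocol Section 6.2.1 to match:
- Include site and race/ethnicity as main effects in the primary GEE logistic model.
- Code race/ethnicity there as Black, Latino, and White/other. The pooled subgroup category would lose most of the gain (step 6).
- Report a covariate-standardised risk difference, which is the scale of the 23-point minimum detectable effect, with the adjusted odds ratio beside it.
- Keep the unadjusted model as supportive.
- Do not add age or prior PrEP use to the primary model. Leave both in the exploratory subgroup analyses.

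The cost is a short insertion in each document. No new data are needed, and the power statement can stay as it is.

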All participants will receive a phone call check-in one week after PrEP initiation to inquire about any side effects or other problems experienced in taking PrEP and provide additional support, if appropriate. Staff will also ask all immediate intervention arm participants about any issues with using the DOT Diary app and provide assistance as needed.

5.6.3 Weeks 6 and 18

At the week 6 and 18 visits, participants will have HIV 4th generation testing and risk reduction counseling performed and their blood collected for DBS. Additional bottles of study drug will be distributed as needed to ensure the participant has adequate supply until the next study visit, accounting for potential missed visits and rescheduling. Participants who are using the app will be asked about any problems or issues with using the app and will provide assistance as needed.

Between all follow-up visits, study staff will reach out to participants by phone or text message in the event of prolonged non-use, multiple overrides of the device, or evidence of suspicious behavior per the *DOT Diary Panel Management and Participant Contact SOP*.

5.6.4 Weeks 12 and 24

In addition to the procedures described at the week 6 and week 18 visits, participants will have blood tests for creatinine, and RPR, as well as urine and oral and rectal swabs for GC/CT at the week 12 and 24 visits. Participants who test positive for STIs will be offered or referred for treatment per local clinic protocol; local guidelines for STI reporting will be followed. They will also complete a CASI assessing sexual and drug use behavior, use of the various components of DOT Diary and acceptability of the app (if they used the app in the past 12 weeks).

At week 12, participants will be dispensed 3 bottles of TDF/FTC (90 pills).

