5.6.6 Microincentives

Microincentives are increasingly being used to support users for their time and effort in using assistive applications in clinical trials and real-world settings.²⁸ Participants in the intervention arm will be provided \$0.50 each day the AiCure system is used for dosing. As participants in the control condition will not be using the AiCure system, they will be asked to track the number of steps they take each day using a fitness app on their smartphone and will be provided \$0.50 each day they send a screenshot from this app via text message to a secure research portal. Participants may also choose a different activity to track each day (e.g. number of hours they slept the night before) and text this information to the study team in the same manner. Intervention participants will be reimbursed every 2 weeks via an electronic payment system linked to the DOT Diary app (based on use of the app during that 2 week period) or receive a lump-sum payment at their next study visit.

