5.6.10 Early termination of study participation

Participants may voluntarily withdraw from the study for any reason at any time. The site investigator may, withdraw participants before their scheduled termination visit to protect their safety or staff safety, and/or if participants are unable or unwilling to comply with study procedures. Participants also may be withdrawn if the study sponsors, government or regulatory authorities (including the OHRP and US FDA), or site IRB terminate the study prior to its planned end date. Study staff will record the reason(s) for all withdrawals in participants' study records. The week 24 visit procedures should be followed when possible, in the event that a participant chooses to withdraw early from the study.

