To evaluate the concordance of TFV-DP and FTC-TP in DBS with adherence measured by DOT Diary. Validation of DOT will focus on concordance between aDOT-based assessments of PrEP adherence by the AiCure device with four DBS measurements. *First*, we will use a pharmacokinetic (PK) model with parameters estimated in the DOT-DBS Study (NCT02022657) to calculate the expected TFV-DP levels when each DBS is obtained, based on the aDOT-confirmed pattern of pill-taking over the previous 6 weeks, as assessed using aDOT-confirmed results. In sensitivity analyses, we will include self-reported pill-taking. We will then estimate the correlation between these predictions and observed TFV-DP levels based on DBS, and scatterplot the two measures against each other, with a Lowess smooth. As an additional measure of concordance, we will estimate the proportion of 90% prediction intervals obtained from the PK model that include the measured DBS TFV-DP levels. **Second**, we will also use aDOT-confirmed aDOT records of pill-taking over the previous 4 and 8 weeks to estimate the average number of PrEP doses per week taken by each participant, then estimate concordance of aDOT- and DBS-based indicators for protective dosing of 4-7 doses/week, with 95% confidence intervals. The DBS indicator will be defined by TFV-DP levels ≥700 fmol/punch. We will also assess concordance of aDOT- and DBSbased measures of <2, 2-3, and 4-7 doses per week, using the Kappa statistic. Third, we will estimate concordance between an aDOT-based indicator for any PrEP use over the previous 48 hours with an indicator for detection of FTC-TP in DBS, again with 95% confidence intervals. Margins of sampling error (MSEs). The expected sample of 240 DBS (an average of 3.59 from each of 67 participants, accounting for cumulative 20% loss to follow-up over 24 weeks) will allow us to estimate the concordance of paired binary measures within MSEs of 6.3-8.4 percentage points, depending on the sample concordance. MSEs for concordance of DOT results with detection of FTC-TP will be similar.

To assess the acceptability and ease of use of DOT Diary over a 24 week period.

Acceptability and ease of use will be measured using the System Usability Scale (SUS) and

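### Does the primary TFV-DP GEE need a stated working correlation, standard-error type and missing-DBS analysis to guard against dropout bias?

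*SAP*

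**What the plan says.** Under Primary Objectives, the SAP (like Protocol 6.2.1) fits GEE logistic models to the repeated TFV-DP indicator by assigned arm, with linear and proportional-odds versions alongside. It plans on a 60% level, an ICC of 0.69 and 80% retention at week 24. On loss to follow-up, the SAP adds for this analysis only: "To help with interpretation of these results, retention in the study will at each 6-week visit will be reported". On time course it says: "In exploratory analyses, we will examine whether the between-group difference increases over time".

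The SAP is more explicit elsewhere. For the secondary GEE on coverage of sexual acts, "robust standard errors will be used to account for within-subject correlation". For daily app use, "In the primary ITT analysis, participants will be included in the denominator through 24 weeks, regardless of dropout". The concordance precision statement builds in the same loss: "an average of 3.59 from each of 67 participants, accounting for cumulative 20% loss to follow-up over 24 weeks".

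The Protocol also deals with loss operationally. Section 4.5 sets a 90% retention goal at the final visit, and section 5.6.10 says of early leavers: "The week 24 visit procedures should be followed when possible, in the event that a participant chooses to withdraw early from the study".

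**The concern.** The primary between-arm estimate has less written about correlation, standard errors and dropout than two secondary analyses. With repeated measures as strongly correlated as ICC 0.69, the working correlation affects more than efficiency. An independence GEE averages whatever DBS are observed. If participants below 700 leave more often, each arm's later visits are enriched with adherent participants, and if the enrichment differs by arm a difference appears with no true effect.

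Arm-specific loss is conceivable. Section 5.6.3 says "study staff will reach out to participants by phone or text message in the event of prolonged non-use, multiple overrides of the device", which concerns app users, while for controls section 5.6.6 says "they will be asked to track the number of steps they take each day using a fitness app on their smartphone". At stake would be a small spurious pooled effect and an apparent benefit that grows with time, which could mislead planning of the larger trial. A retention table corrects neither.

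**Working it through.** **1. The plan's own figures.** Inputs: 67 and 33 participants (Protocol 5.3); 60%, ICC 0.69, 80% retention, 5% two-sided, 80% power, 23 points (SAP). With everyone seen at week 6 and a constant rate of loss afterwards, mean DBS per person is 1 + 0.8^(1/3) + 0.8^(2/3) + 0.8 = 3.59, and 3.59 × 67 = 240.5, matching the stated 240.

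Variance factor: (1 + 2.59 × 0.69)/3.59 = 0.776. Effective sizes: 33/0.776 = 42.5 and 67/0.776 = 86.3. For 60% against 83%, with the pooled-variance test, power is 0.800. The 23-point figure reproduces.

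**2. Yardstick.** With 60% in both arms, SE = √[0.24 × (1/42.5 + 1/86.3)] = 9.2 points. The planning alternative implies 23/2.80 = 8.2.

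**3. Bias with no true effect.** Assumed: 60% protected, ICC 0.69, no loss at week 6, overall loss 20% (for example (2 × 25 + 10)/3 = 20). Participants whose last DBS was below 700 are 2 or 6 times as likely to leave. Simulation with 2,000,000 per arm; bias in percentage points (2-fold / 6-fold):

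| App/control loss | Independence | Exchangeable |
|---|---|---|
| 20/20 | about 0 | about 0 |
| 22/16 | +0.4 / +1.0 | within 0.2 |
| 23/14 | +0.6 / +1.5 | within 0.2 |
| 25/10 | +0.9 / +2.6 | within 0.2 |
| 15/30 | -1.1 / -2.7 | within 0.2 |
| 25/10, dropout on the unseen current DBS | +1.2 / +3.1 | +0.4 / +1.1 |

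At 25/10 with 6-fold dropout on the last DBS, independence shows differences of 0.1, 2.0, 3.8 and 5.5 points at weeks 6, 12, 18 and 24. Exchangeable shows 0.1 to 0.2 throughout.

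Loss need not differ in amount. At 20/20, with 6-fold dependence in the app arm and none in control, independence gives about +3.0 points and exchangeable about 0.

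If retention came nearer the 90% goal (12.5/5), the independence bias would be +0.5 / +1.2.

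**4. Effect on inference.** A 2.7-point bias is 2.7/9.2 = 0.29 SE, which raises type-I error from 5% to about 6.0%; with SE 8.2 it is about 6.2%. In simulated null trials of 67 and 33:

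- Independence with robust SEs rejected in 5.1% under random loss. With app-arm loss of 35% below 700 and 10% above, and random 20% loss in control, it rejected in 6.9% when loss depended on the current value.
- Exchangeable rejected in 4 to 7% throughout, with robust or model-based SEs.
- Independence with model-based SEs rejected in about 25% even under random loss.
- The arm-by-time test under independence rejected in 6.0% with random loss and 10 to 11% in the moderate informative scenarios.

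**5. What added analyses would do.**

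- Retention weights give bias within 0.1 when dropout depends on earlier DBS, no real gain over exchangeable. When it depends on the unseen current value at 25/10, they give +0.6 to +1.6, somewhat worse than exchangeable.
- Counting missing DBS as below 700 gives -2.6 to -3.9 points under a true null at 25/10. With equal loss it shrinks 23 points to 23 × 3.59/4 = 20.6 and cuts simulated power from 75.6% to 67.1%.

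**The case for a change.** The strongest case for a change has four parts.

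- **The choices are unwritten.** An analyst could use independence, and with model-based SEs the false-positive rate is about 25%. That stands as arithmetic. But robust SEs are the usual GEE default and the SAP names them for its other GEE, so that pairing is improbable.
- **Equal retention percentages can hide the problem**, as the 20/20 case with unequal dependence shows. This is correct, and the retention table would not reveal it. It still biases the pooled estimate only under independence when dropout depends on earlier DBS.
- **Exchangeable is not a full cure** when dropout depends on the unseen current value. This also stands. The residual is 0.4 to 1.1 points at 25/10, and retention weights do not reduce it.
- **Worse cases can be built.** If half of those below 700 in the app arm leave and none of the others do, against random 20% loss in control, independence gives 6.1 points pooled (11.9 at week 24) and exchangeable 2.1. The arm-by-time test under independence then rejects in 27.6% of null trials. Nothing in the documents points to a mechanism that strong.

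The week to which an exit DBS is assigned is also unstated, but analysts can settle that sensibly from the collection date.

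**Conclusion.** This is a gap in detail that competent analysts fill sensibly. The SAP plans around a within-person ICC of 0.69 and names robust standard errors for its other GEE. Neither settles the primary model, but both point to the ordinary choice of exchangeable correlation with robust errors. Under that choice the pooled bias is within 0.2 points for dropout on earlier DBS and about 1 point for dropout on the unseen current value at 25/10.

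Even under independence, the plausible scenarios give about 0.4 to 3 points, at most about a third of a standard error, with the direction unknown. The time trend is labelled exploratory, and the 90% retention goal and exit procedures would reduce the bias further. The candidate additions offer no net gain: weighting adds almost nothing, and counting missing as below 700 substitutes a bias of similar or larger size in the opposite direction.

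These sizes rest on assumed loss by arm and assumed dependence of dropout on adherence, since the documents give only overall retention. The 23-point detectable effect stands.
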